Patients are treated with octagam®, panzyga® or cutaqui® according to the Investigator's prescription. For dosage recommendations please refer to the local octagam®, panzyga® or cutaqui® package leaflets.

Dosage and duration of treatment is at the sole discretion of the Investigator and will depend on the type and/or severity of the disease and the patient's clinical condition.

In case of SCIG home treatment the Investigator should promote compliance by instructing the patient to take cutaqui[®] exactly as prescribed and by stating that compliance is necessary for the patient's safety. The patient should be instructed to contact the Investigator if he/she is unable for any reason to administer cutaqui[®] as prescribed.

All dosages of octagam[®], panzyga[®] or cutaqui[®] that a patient received during the observation period at the study center are to be recorded on the corresponding eCRF pages. Dosages of cutaqui[®] that a patient administered during the observation period at home are to be recorded in the patient diary and will be entered into the eCRF later. It is of utter importance that all data entered into the diary are checked by the Investigator for completeness and any safety-relevant issues (including infusion site reactions) during each patient's visit to the study center.

Any drug dose adjustment and interruptions should be recorded on the corresponding eCRF page.

If, for any reason, the Investigator or the patient decide to discontinue the treatment with octagam[®], panzyga[®] or cutaqui[®], the observation period of this patient will be terminated. Efforts should be made to arrange a close-out visit. The reason(s) for termination in the eCRF is to be documented. Switching from one Octapharma Ig product to another Octapharma Ig product is possible without termination of the study but should be documented.

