5.1 ADVERSE DRUG REACTION

An ADR is any noxious and unintended response to the study drug which occurs at doses normally used in humans for the prophylaxis or therapy of disease or for the restoration, correction or modification of physiological function. Response in this context means that a causal relationship between the study drug and an adverse event (AE) is at least a reasonable possibility.

Serious ADR

A serious ADR is any untoward medical occurrence that is considered related to study drug and that at any dose:

- is resulting in death;

- is life-threatening ("life-threatening" means that the patient was at an immediate risk of death at the time of the event; it does not mean a hypothetical situation of what could or would have happened if, for example, no treatment had been administered);
- requiring hospitalisation or prolongation of existing hospitalisation (hospitalisation does not refer to the treatment of an ADR on an out-patient status);
- resulting in persistent or significant disability/incapacity;
- is a congenital anomaly/birth defect;
- is any other important medical event (e.g. suspected transmission of an infectious agent, or other reactions that should be reported in an expedited manner although they did not immediately result in one of the above seriousness criteria).

Medical judgment should be exercised in deciding whether an ADR is serious in other situations: Important ADRs that are not immediately life-threatening or do not result in death or hospitalization but may jeopardize the patient or may require intervention to prevent one of the other outcomes listed in the definitions above, should also be considered serious.

Causality assessment of cases should follow the WHO-UMC causality categories: <https://www.who-umc.org/media/2768/standardised-case-causality-assessment.pdf>

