5.2 OTHER RELEVANT DRUG SAFETY INFORMATION

The following events should also be reported:

- a) pregnancies/breastfeeding;
- b) drug abuse (persistent or sporadic, intentional excessive use of a medicinal product, which is accompanied by harmful physical or psychological effects), misuse;
- c) overdose (treatment exceeding the medically recommended dose);
- d) medication errors (prescribing or dispensing error);
- e) interaction(s) with other medicinal product or device;
- f) suspected transmission of infectious agent;
- g) off-label use;
- h) occupational exposure;
- i) lack of efficacy;
- j) quality complaints with harm (or potential harm) of the patient.

This information should be reported if associated with the use of octagam®, panzyga® and/or cutaqui® or – in case of pregnancy/breastfeeding – if observed during treatment with octagam®, panzyga® and/or cutaqui®.

Above mentioned events should also be recorded if no ADR occurred.

In the eCRF specific pages are included for data entry for ADRs and infusions site reactions.

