5.3 REPORTING OF ADRS AND OTHER SAFETY INFORMATION

All ADRs and other safety information as defined above have to be documented on the specific electronic forms of the electronic data capturing (EDC) system.

Serious ADRs have to be entered *immediately* (within 24 hours) into the eCRF and should be transferred electronically to Octapharma.

Non-serious ADRs and other safety information should be reported upon recognition but no later than 10 days.

Patients undergoing home treatment should be asked to inform their treating physician immediately of any ADR, or other relevant safety information. The treating physician will assess the causal relationship for ADR and report the event as described above.

Octapharma will handle all ADRs as post-marketing safety reports and will report the cases in compliance with applicable regulations for pharmacovigilance.

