### 3.4 Primary endpoint(s)

The primary endpoint of this study is the incidence (count and frequency) of ADRs.

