### **6.2.2 Handling of missing or incomplete dates**

For the determination whether an Individual Case Safety Report (ICSR, see section 7.6.1 for the definition) as denoted on the ADR form that has a missing or incomplete start date might not qualify as on-study-case the following rules will be applied:

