### 7.6.1 Individual Case Safety Reports (ICSRs) and Adverse Drug Reactions (ADRs)

There will be a clear differentiation between ‘cases’ and the individual symptoms reported. This distinction is reflected in the eCRF by the possibility to enter several symptoms on a single ADR form. The following terminology is used in this document to clearly reflect this differentiation:

ADR = A single symptom or term reported; always coded to an individual MedDRA preferred term (PT).

Individual Case Safety Report (ICSR) = All reported symptoms or terms that are related to one and the same infusion (except re-challenges – to be counted also as one ICSR).

The assessment of severity and relatedness to study drug will be done on the case level.

For all analyses (except the listing of ICSRs leading to death), cases recorded on the ADR form of the eCRF but rated as “not related” will be excluded. Further, cases recorded on the ADR form but with a start date before the first IVIG/SCIG infusion will be excluded from all summaries as well but will be included in the listings if not rated as “not related”.

An overview table will show the count and percentage as well as the number of ICSRs regarding the occurrence of any ICSR, any serious ICSR, and any ICSR leading to withdrawal of study drug by treatment group and overall. Percentages will be calculated with two different denominators:

- Number of patients in the respective treatment group

- Number of infusions in the respective treatment group.

This overview table will also be presented by diagnosis.

The tabulation of count and percentage of ADRs and serious ADRs will be based on PTs and SOCs of the MedDRA thesaurus. MedDRA version 23.0 will be used for coding. Percentages again will be calculated based on the number of patients and on the number of infusions by treatment group and overall.

These summaries of ADRs will also be presented by diagnosis, by country (Austria, Spain, France, UK and Canada) and by age group (age categories < 18, 18-43, 44-68, and > 68 years).

All ICSRs will be listed, in addition, there will be separate listings for

- ICSRs leading to death (this listing will also include cases rated as “not related”).
- Serious ICSRs
- ICSRs leading to withdrawal of study drug.

In summaries by SOC and PT, ADRs will be sorted by decreasing frequency in the overall group by SOC and then by PT within SOC.

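### Could infusion site reactions be lost from, or counted twice in, the ADR tables because the SAP's rules name only the ADR form?

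*SAP*

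**What the plan says.** SAP 3.4 is short: "The primary endpoint of this study is the incidence (count and frequency) of ADRs". SAP 3.7 makes the safety endpoint the same.

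The SAP's handling rules are tied to the ADR form:

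- SAP 6.2.2 applies date imputation to a case "as denoted on the ADR form that has a missing or incomplete start date".
- SAP 7.6.1 explains the difference between a case and its symptoms by the option to "enter several symptoms on a single ADR form".
- SAP 7.6.1 excludes from all analyses, apart from the listing of fatal cases, those "cases recorded on the ADR form of the eCRF but rated as" not related.
- SAP 7.6.1 also excludes from the summaries ADR-form cases that began before the first infusion.

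The Protocol says more about where safety data are entered. Section 3.1.3 gives the eCRF four main sections (baseline, treatment record, suspected ADRs, efficacy) and assigns suspected ADRs to ADR forms. Section 5.2 ends with the sentence "In the eCRF specific pages are included for data entry for ADRs and infusions site reactions". Section 5.3 opens with "All ADRs and other safety information as defined above have to be documented on the specific electronic forms". Section 4.1 gives infusion site reactions as an example of what the investigator should look for when checking home-treatment diaries.

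**The concern.** The Protocol mentions infusion site reactions twice (4.1 and 5.2), and 5.2 can be read as describing a page of their own. The SAP refers to the ADR form four times and to infusion site reactions not at all. If a second page exists, a programmer following the SAP finds no statement on whether its entries feed the ADR tables, whether the relatedness and start-date exclusions apply to them, or how to treat a reaction that appears on both pages.

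The primary endpoint would be at stake. Reactions held only on a second page would be missing from ADR incidence, and reactions held on both and simply pooled would inflate the number of ADR terms. The tables are by treatment group and the Protocol raises site reactions in its text on subcutaneous home treatment, so one could also suspect an uneven effect across products.

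**Working it through.** The documents give no ADR or infusion site reaction rate, so there is no figure to reproduce. The check follows one local reaction through the two documents.

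**Word count.** SAP, ADR form: 1 (section 6.2.2) + 3 (section 7.6.1) = 4. SAP, infusion site: 0. Protocol, infusion site reactions: 1 (section 4.1) + 1 (section 5.2) = 2. The contrast in wording is real.

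**Route of a related local reaction.**

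1. *Is it an ADR?* Protocol 5.1 asks whether "a causal relationship between the study drug and an adverse event (AE) is at least a reasonable possibility". It makes no exception for reactions at the infusion site, so a related local reaction is an ADR.
2. *Where is it entered?* Protocol 3.1.3 sends suspected ADRs, during or after administration, to ADR forms. Its four main eCRF sections include none for infusion sites. The 5.2 sentence fits one shared set of pages as well as two sets, and nothing in it releases a related reaction from the 3.1.3 rule.
3. *What about home treatment?* Patients note every ADR in the diary (3.1.3) and the investigator checks the diary at visits (4.1). Patients also tell the physician, who judges causality and reports through the same system (5.3). The route ends at the same form.
4. *How is it counted?* Under SAP 7.6.1 each reported symptom is one ADR with its own MedDRA preferred term, and all symptoms tied to the same infusion form one case. A local symptom is handled like a systemic one, and appears in the SOC and PT tables by treatment group.
5. *Which exclusions apply?* The relatedness rule, the start-date rule and the date imputation all operate on the ADR form, which is where step 2 placed the reaction.

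**Count per related reaction (ADR terms / patients affected / infusions affected).**

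| Situation | Count | What it requires |
|---|---|---|
| ADR form only | 1 / 1 / 1 | Protocol 3.1.3 followed |
| Both pages, ADR form as source | 1 / 1 / 1 | A second page exists |
| Both pages pooled, not reconciled | 2 / 1 / 1 | A second page exists, plus pooling that the SAP does not describe |
| Second page only, ADR form as source | 0 / 0 / 0 | A second page exists, plus a site not following Protocol 3.1.3 |

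The first row is the plan as written: 1 − 1 = 0 change in every count. The second row shows that a second page alone does no harm. The last two rows each need a second page and a further step that departs from the documents.

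**Local reactions judged not related.** These are not ADRs under Protocol 5.1 and do not belong in the primary endpoint, so leaving them out of the ADR tables is correct.

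**The case for a change.** The best argument on the other side is that the SAP states how other safety data are handled (laboratory results listed but not tabulated in 7.6.2, pregnancy entries listed only in 7.6.4) yet says nothing about a type of entry for which the Protocol names eCRF pages. Section 8, on changes from the Protocol, does not mention dropping them either. A listing under SAP 7.1 does not define what counts in the primary endpoint, and templates kept in a separate document (SAP 1) cannot be assumed to fill a gap.

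Part of this stands. The 5.2 sentence can be read as a separate page, and the SAP does not mention one. The point about listings is also fair, and the conclusion here does not rest on listings or on the templates.

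The comparison with laboratory and pregnancy data does not carry over. Those data lie outside the ADR tables and so need their own statement. A related local reaction lies inside them by definition and is covered by the general ADR rules. The suggestion of an uneven effect on the subcutaneous product rests on a diary-checking instruction that contains no rate, so it has no size. Any illustration of understated incidence needs an assumed share of patients whose only reaction sits on a second page. That share is zero if sites follow Protocol 3.1.3.

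**Conclusion.** The concern does not hold. The SAP ties its case structure, both exclusion rules and its date imputation to the ADR form, and the Protocol puts every related local reaction on that form. Followed as written, the plan counts each such reaction once, and the effect on ADR counts is 0.

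This rests on two assumptions: that sites enter suspected ADRs where Protocol 3.1.3 tells them to, and that the 5.2 sentence does not override that rule. The eCRF and the table templates were not available, so whether a separate infusion site page exists is unknown. That can be asked of whoever holds the eCRF. An extra sentence naming the source form would be a matter of preference, since it would restate what the rules already imply and would alter no result shown in the documents.

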3.1.4 Study Duration

This study started in August 2011 in 4 European countries and was then extended to Canada. The European centres are now closed or being closed and the study will continue in Canada. Planned study end is 2022.

The duration of observation for an individual patient will be as long as any of the described IVIGs or the SCIG will be prescribed by the treating physician and until the next regularly scheduled visit of the patient after last infusion. For patients with PID or SID the observation period should last at least 12 months, if possible.

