## **3 STUDY DESIGN**

### **3.1 General study design**

This is a prospective, multicentre, non-interventional study (NIS).

The treating physician decides whether, how and for how long a patient is to be treated with octagam®, panzyga®, and/or cutaquinig®.

octagam®, panzyga®, and/or cutaquinig® will be prescribed regularly to any patient who needs to be treated with an IgG product because of their medical condition and whom the treating physician wants to include in this observational study, after the decision has been made to prescribe IVIG or SCIG treatment. This study will observe 300-500 patients treated with octagam®, panzyga® and/or cutaquinig® in any indication, age group, gender or treatment regimen. It is not possible to specify the exact number of doses per patient that are to be documented because of the different indications for use.

This observational study is conducted in outpatient and inpatient centres globally.

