## **7 STATISTICAL METHODS**

### **7.1 General statistical conventions**

All statistical procedures will be completed using SAS version 9.4 or higher.

Continuous variables will be summarized using descriptive statistics, including number of subjects (n), mean, median, standard deviation (SD), minimum and maximum.

For categorical variables, summaries will include counts of patients and percentages. Percentages will be rounded to one decimal place.

All summaries will be presented by treatment group and overall, unless otherwise specified. As patients are allowed to change the study drug during the course of the study, treatment groups can be defined that are composed of more than one treatment depending on which patterns of treatment change will actually be observed. In case that such treatment groups are defined, summary tables by visit or summary tables for events that occur within the study will contain more than one column for these composed treatment groups. A patient will be summarized in the column that belongs to the actual treatment that the patient received at the respective visit or at the onset of the respective event.

All patient data, including those derived, will be presented in individual patient data listings. Unless otherwise stated, unscheduled visit results will be included in date/time chronological order, within patient listings only. All listings will be sorted by centre, patient number, date/time and visit (if applicable). The treatment group as well as patient's sex, age and diagnosis will be stated on each listing. Unless otherwise stated, data listings will be based on the Safety population.

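### Does giving ADR percentages on both patients and infusions, without naming a numerator for each, make the infusion percentage misleading?

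*SAP*

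**What the plan says.** SAP section 3.4 sets the endpoint: "The primary endpoint of this study is the incidence (count and frequency) of ADRs". It does not say whether the unit is a patient, a reaction or an infusion.

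Section 7.6.1 then describes two kinds of table.

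- **Overview table.** "An overview table will show the count and percentage as well as the number of ICSRs regarding the occurrence of any ICSR", with the same for serious cases and for cases leading to withdrawal of the drug. "Percentages will be calculated with two different denominators": patients in the treatment group, and infusions in the treatment group.
- **Term tables.** "The tabulation of count and percentage of ADRs and serious ADRs will be based on PTs and SOCs of the MedDRA thesaurus". The next sentence but one is "Percentages again will be calculated based on the number of patients and on the number of infusions by treatment group and overall". These tables are repeated by diagnosis, country and age group.

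The same section defines its units. An ADR is one reported symptom or term. An individual case safety report (ICSR) gathers all symptoms belonging to one infusion, with an exception for re-challenges.

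The general convention in section 7.1 reads: "For categorical variables, summaries will include counts of patients and percentages". Section 1 places the table templates in a separate document, which was not available here.

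**The concern.** The term tables name one count and two denominators. Read together with the section 7.1 convention, that count would be patients, and the infusion percentage would be patients with the reaction divided by infusions. A patient enters the numerator at most once, while every one of that patient's infusions enters the denominator. The result is not a rate per infusion: it has a ceiling, and at equal risk it falls as patients receive more infusions.

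Taking the count as reactions instead repairs the infusion figure but spoils the other one. Reactions over patients is not a share of patients and can pass 100%.

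The tables carry the primary endpoint, and no hypothesis test stands behind them, so the percentages are themselves the result. They are also set side by side across groups whose infusion numbers may well differ. The SAP says of dosing that "It is not possible to specify the exact number of doses per patient" because indications vary, and protocol section 3.1.4 adds a target for immunodeficiency patients: "For patients with PID or SID the observation period should last at least 12 months, if possible". If patients were divided by infusions, a group with more infusions per patient could look safer for that reason alone.

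**Working it through.** The documents state no percentage to reproduce. The inputs are N patients (300 to 500, SAP section 4), a mean of m infusions per patient (at least 1 by the Safety population definition in section 5.2, otherwise not given), and a reaction risk p per infusion (not given). Values of m and p below are assumptions.

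**1. The ceiling.** Let x be the number of patients with the reaction. Infusions total N × m, so

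100x/(N × m) = (100x/N)/m ≤ 100/m.

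N cancels. The ceiling is 25% at m = 4, 7.69% at m = 13 and 1.92% at m = 52. The identity is exact, but it holds only if patients are the numerator.

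**2. How far below the true rate.** Suppose each patient has n infusions, with the same independent risk p at each. The expected share of patients affected is 1 − (1 − p)^n, and patients over infusions is that divided by n.

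| True risk p | n = 4 | n = 13 | n = 52 |
|---|---|---|---|
| 1% | 0.99% | 0.94% | 0.78% |
| 2% | 1.94% | 1.78% | 1.25% |
| 5% | 4.64% | 3.74% | 1.79% |

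The relative shortfall runs from 1.5% (p = 1%, n = 4) to 64% (p = 5%, n = 52). At n = 1 there is none. For a rare term (p = 0.2%, n = 13) the figure is 0.198%, a shortfall of 1.2%.

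Clustering makes it larger. If 20% of patients carry all the risk (5% per infusion in them, mean 1%), the figures are 0.93%, 0.75% and 0.36%.

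Group order can reverse: p = 2% at n = 4 gives 1.94%, while p = 4% at n = 52 gives 1.69%. It need not: p = 1% at n = 4 gives 0.99%, against 1.25% for p = 2% at n = 52.

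**3. The other single count.** With one reaction per affected infusion, reactions over patients is n × p. At p = 2% and n = 52 that is 104%, against 65% of patients truly affected.

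**4. The ordinary pairing.** Take N = 300 and m = 13, so 3,900 infusions, and let 60 patients react at every infusion, giving 60 × 13 = 780 reactions.

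| Numerator and denominator | Result |
|---|---|
| Patients over patients | 60/300 = 20.0% |
| Reactions over infusions | 780/3,900 = 20.0% |
| Patients over infusions | 60/3,900 = 1.54% |
| Reactions over patients | 780/300 = 260% |

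The first two rows are sound. The last two arise only if one count is forced onto both denominators.

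**5. Which pairing the text supports.** The overview sentence names two quantities, a count and, separately, the number of ICSRs, and then two denominators. An ICSR is built around one infusion, so its natural denominator is infusions. The paragraph on the term tables says percentages are again formed on both denominators, which carries the same scheme over. There the unit is the ADR, defined as a single symptom, which is an event. No sentence says that one count must serve both.

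**The case for a change.** The strongest counter-argument is that a SAP should not need interpretation where it describes the primary tables. Section 1 promises detailed descriptions of methods and derivations. The infection analyses in section 7.5.2 do separate patients with episodes from the total number of episodes, and the ADR term tables do not. Section 7.1 points towards patient counts, and its rule for patients who change product also speaks of placing a patient in a column. Two programmers could in principle produce different tables.

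What stands is that section 7.6.1 leaves the numerators of the term tables unassigned, and one sentence would have settled it. What does not stand is the step from there to a faulty analysis. The specific definitions in 7.6.1 would normally prevail over a general convention for categorical variables, and an infusion denominator is itself a strong signal that events are being counted. The templates, where row and column numerators are usually fixed, may already say so.

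The rows with potentially the largest gap, those for any case, sit in the overview table. That table prints the number of ICSRs, and section 7.4.2 summarises infusions per patient by treatment group and by diagnosis, so a reader could rebuild the rate for those groups. That help does not extend to country or age group, for which 7.4.2 plans no exposure summary. The contrast in exposure between diagnoses is also less certain than it seems: protocol section 3.1.4 observes every patient for as long as treatment is prescribed, and the 12 months is an added target where possible.

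**Conclusion.** No change to the plan follows. The ceiling of 100/m is exact, but it applies to a calculation that the SAP does not prescribe. It appears only when the general convention of section 7.1 is imposed on tables for which section 7.6.1 supplies its own event units. The sound pairing is consistent with the text, needs no data beyond those already planned, and is the one an analyst would normally choose.

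Even on the unfavourable reading, the per-patient percentages and the listings would be correct, and no test would be affected. The relative error in the infusion figures would range from about 1% for rare terms to 64% in the most extreme case shown with uniform risk (p = 5%, n = 52). Both ends rest on assumed infusion numbers and risks. The conclusion assumes that the programmed tables pair patients with patients and events with infusions; the table templates would confirm this.
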